involved with this study and can objectively evaluate the patient) to determine if the patient should be removed from the study to receive alternative, or more intensive care. The PI and [name] will coordinate care, either at CARD or elsewhere, for participants withdrawn due to deterioration. After completion of the study, *all* participants will be given a written list of referrals and instructions to contact study staff if they would like assistance with securing additional treatment. It should be noted that patients in dire need of additional treatment (likely due to deterioration because only stable patients will be recruited) will have been withdrawn at this point; this is a longstanding procedure within collaborator [name] lab for providing resources to patients completing research trials. Participants' confidentiality will be carefully guarded and respected. Data will be coded with participant numbers, with all identifying information removed. Data with identifying information will be stored in locked cabinets and electronic data will be password protected on secure CARD servers.

**DATA ANALYSIS: PHASE I & II.** *Phase I Data Analyses:* Hypotheses regarding differential outcomes between the two strategies (acting consistent versus inconsistent) will be evaluated using a combination of classical methods of idiographic data-analysis and modern non-parametric statistical techniques. We will first plot parallel lines representing intensity of emotion as a function of each individual strategy. These will be directly compared as to changes in level and slope. In addition to customary visual observation (often, functions in ATDs yield non-overlapping datasets), more quantitative evaluations will also be employed by conducting non-parametric randomization and bootstrap tests of the mean differences between the two conditions. The non-parametric statistical analyses will be conducted using the Single-Case Randomization Tests package (SCRT) within the R statistical framework. Randomization tests will be conducted regarding levels of mean change in self-reported emotional intensity and clinician-rated facial emotional intensity from post-induction to post-regulation condition (acting consistent/inconsistent). Results from these non-parametric randomization tests will be used in conjunction with the visual observations for each individual to draw conclusions regarding the effect of acting counter to EDBs on the intensity of emotion relative to acting consistent with emotional urges.

*Phase I, Hypothesis 1:* When instructed to respond to induced emotions by acting inconsistent to emotional urges, participants will demonstrate greater reductions in the intensity of their emotions compared to acting consistent with their emotional urges. Similar patterns of results are expected across all discrete emotions induced.

*Phase II Data Analyses:* The multiple baseline and phase change design will make between- and within-subjects analysis possible. By applying different baseline lengths across individuals, between-series comparisons will be possible to determine if changes in EDBs, emotional intensity, and emotional tolerance occur when and only when the intervention is applied. The phase change (baseline phase to treatment phase) process will allow for within-series comparisons to examine concomitant changes in EDBs, emotional intensity, and emotional tolerance when treatment is present compared to when it is absent within individuals. For both between-and within-subjects comparisons, we will first plot parallel lines representing changes in these variables over time for each individual. These will be directly compared in terms of changes in level and slope to determine if differences seen are due to phase change. We will also conduct non-parametric randomization tests of mean differences in EDBs, emotional intensity, and emotional tolerance as a function of phase using the SCRT within the R statistical framework. Results from these tests will be used with visual inspection of data to draw conclusions regarding effects of the intervention on frequency of EDBs, emotional intensity and emotional tolerance. We will also explore maintenance effects of our intervention by examining stability in EDBs, emotional intensity, and emotional tolerance during the follow-up phase. Finally, as an exploratory analysis, we will examine phase effects (baseline, treatment, follow-up) on clinician rated and self-reported BPD symptoms.

*Phase II, Hypothesis I:* Individuals will demonstrate change in self-reported frequency of EDBs, intensity of emotion (PANAS) and tolerance of emotions (MEAQ), as well as behavioral willingness to act inconsistent with emotional urges (PASAT-C) only after treatment is applied. *Phase II, Hypothesis II:* Change in these variables will be maintained during a 4-week follow up period. *Phase II, Hypothesis III:* In this exploratory analysis, we hypothesize that clinician-rated and self-reported BPD symptoms (ZAN-BPD, ZAN-BPD-srv) will decrease when and only when the intervention is applied, and only for patients who demonstrate reduction in EDBs.

*Power Analyses.* Sample size in SCEDs refers to the number of observations collected. In Phase I, 35 observations (ratings of emotional intensity) will be collected for each emotion under study (18 acting consistent with emotional urges and 18 acting inconsistent); this will yield 180 total observations with 90 in each condition. Phase II will result in 88 observations for weekly measures and 616 observations for daily

measures. These numbers of observation will make possible detection of medium effect sizes across both phases.

**Timeline Timetable:** Support is requested for 4 years in order to successfully complete both phases of the project, which are integral to the applicant's training goal to gain expertise in exploring mechanisms of action in treatment. Year 1 of the project will be dedicated to acquiring advanced training in the assessment of physiological and behavioral indicators of emotion to corroborate self-report data and for training study staff. Recruitment and data collection for Phase I will take place in Year 2. Recruitment and data collection for Phase II will begin in the 9th month of Year 2 and continue through Year 3. Additionally, in Year 3, data analyses will be started and an R01 application for a larger-scale efficacy trial examining the effect of countering EDBs on BPD symptoms will be submitted. A larger N will make possible longitudinal repeated-measurement of treatment mediators and exploration of moderators (e.g., severity). Finally, Year 4 will be used to complete data analyses, prepare manuscripts, and re-submit the R01 application.

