**PHASE 1: ATD Component Procedures.** Twenty-four participants will be included in the ATD component of this study. There are four discrete emotions (anger, sadness, anxiety, and guilt) under investigation and participants will be randomly assigned to complete study procedures for only one emotion. Six participants will be assigned to each emotion condition. Following usual and customary procedures for ATDs, the first participant for each discrete emotion will comprise the main experiment with the subsequent participants serving as replications. Each participant will be presented with six emotion inductions (focused on the emotion related to their assigned condition), occurring on six separate days over the course of two weeks. In order to maximize clinical relevance, emotional stimuli used in the emotion inductions will be tailored to each individual by instructing participants to write about a time in the past two months in which they felt the particular emotion being induced. This strategy has been successfully implemented previously by the PI to induce strong emotions in individuals with BPD. Prior research has suggested that using idiographic stimuli (vs. standardized stimuli) results in greater emotional reactivity in individuals with BPD and anxiety disorders. Prior to the first emotion induction in the first session, study staff will assist participants in developing a list of situations, occurring in the past two months, that brought up the emotion consistent with the condition to which the participant is assigned. Participants will be asked to rate the emotional intensity of each situation (on a 1-100 scale consistent with subjective units of distress) and six situations rated above 60 (to ensure sufficiently strong emotion is induced) will be chosen as the basis for the emotion induction writing assignments.

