Following each emotion induction, participants will be instructed to either act consistent or inconsistent with the emotion induced; instructions will be randomly alternated so that each participant will act consistent during 3 sessions and act inconsistent during 3 sessions. The randomization schedule will be such that one condition will not be presented more than two times in a row. Participants will be informed that “the goal of this project is to test out two different strategies for coping more effectively with emotions in order to ascertain the most effective strategy for you.” The two conditions will both be presented as credible and effective strategies to the participants in order to minimize any biased results due to expectancy effects. The specific instructions for acting inconsistent and consistent with EDBs following the mood induction will be based on idiosyncratic action urges associated with the induced emotions. For example, the guilt induction may elicit action urges to withdraw/hide and/or (albeit less commonly) lash out in an effort to deflect blame. Acting inconsistent to urges to withdraw may involve making plans with friends (via phone or email) or making small talk with confederates while acting inconsistent to urges to lash could include writing thank you notes to loved ones or engaging in an act of kindness. Study staff will assess for idiosyncratic emotion-driven action urges after the emotion induction to craft appropriate behavioral instructions relevant for the individual.

An important advantage of SCEDs is that the flexible nature of these studies and the immediate availability of results allows for the real-time alteration of procedures in order to obtain an effect on the putative mechanism of action. In this case, if we fail to find reductions in the intensity of the induced emotion by asking participants to act inconsistent with their reported action urges, we may, for example, extend the purview of behaviors to include emotion-consistent/inconsistent posture, and tone of voice. Making these changes informs the development of interventions by evaluating various strategies to manipulate putative mechanisms. The strategies tested can be confirmed by replication and also associated with individual characteristics. Participants will be paid \$40 per session for a total of \$240 for completing the entire six study sessions.

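### Phase I procedures may be altered until an effect appears, and the plan does not separate choosing an altered version from testing it

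*Combined protocol and SAP*

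**What the plan says.** All references are to the combined protocol and SAP.

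**Design (PHASE 1: ATD Component Procedures).** There are four emotions and 24 participants: "Six participants will be assigned to each emotion condition". Within a person, "each participant will act consistent during 3 sessions and act inconsistent during 3 sessions", in random order with no condition given more than twice running. On replication, "the first participant for each discrete emotion will comprise the main experiment with the subsequent participants serving as replications".

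**Alteration (same section).** Flexibility and immediately available results are presented as an advantage of single-case designs because they permit "real-time alteration of procedures in order to obtain an effect on the putative mechanism of action". The trigger is "if we fail to find reductions in the intensity of the induced emotion by asking participants to act inconsistent with their reported action urges", and the response is that "we may, for example, extend the purview of behaviors to include emotion-consistent/inconsistent posture, and tone of voice". On confirmation the text says: "The strategies tested can be confirmed by replication". It gives no threshold for failure, no point at which a change may or may not be made, no closed list of changes and no maximum number of versions.

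**Analysis (Phase I Data Analyses).** Each individual's data are plotted and given a randomization test, and the two are read together. Hypothesis 1 is directional and refers to no version of the procedure. The section does not mention alterations, version labels, or how results from different versions are combined or kept apart.

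**The concern.** The Study Overview gives Phase I the task of testing, for the first time, whether acting against emotional urges lowers emotional intensity. A test of that kind needs the thing tested to be fixed before the data that judge it are seen. Here the outcome that prompts a change can also be the outcome on which the changed procedure is judged. Facial recordings are coded afterwards (Phase I Assessment), so of the two tested indices self-report is the one likely to be available in time to prompt a change, and it is itself a tested outcome.

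Three things follow if a change is made:

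- Participants who showed nothing can be set aside as belonging to an abandoned version. A single favourable participant then stands as 1 of 1 for the new version, where under a fixed procedure the same result would read as 1 of 6.
- Participants enrolled after the change no longer replicate the version that the first participant received, although the design counts them as replications.
- If the change falls inside one person's six sessions, that person's 3 v 3 comparison mixes versions.

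At stake is how far a favourable Phase I conclusion about the mechanism can be trusted.

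**Working it through.** The plan states no error rate for the alteration procedure, so there is no figure of its own to reproduce on this point. Power Analyses gives observation counts only, and they are not used here.

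**Inputs from the plan:** 6 participants per emotion, 4 emotions, 6 sessions per person split 3 and 3, no run longer than two.

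**Assumptions not in the plan:** independent sessions, no true effect, one outcome index, complete non-overlap in the predicted direction as the sign of success, 2 to 4 versions, one participant per version. The plan mentions non-overlap as common in such designs but does not make it a decision rule.

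**1. What one participant can show.** There are C(6,3) = 20 ways to place three sessions of one condition among six. Under no effect each is equally likely to hold the three largest reductions, so P(complete non-overlap, predicted direction) = 1/20 = 5.0%. A simulation of 400,000 null participants gave 4.97%.

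The run rule removes sequences with three in a row: 4 with one condition in a block, 4 with the other, 2 counted twice. That leaves 20 − (4 + 4 − 2) = 14. The smallest one-sided randomization p for one person is 1/14 = 0.071. No single participant can reach 0.05, so crediting a version on one person rests on visual judgement or a looser cut-off.

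**2. Chance that at least one of k null versions looks effective.** P = 1 − (1 − p)^k. The last column multiplies the non-overlap figure by 1/20, which requires the next participant under the same version to show non-overlap too.

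| k versions | p = 1/20 (non-overlap) | p = 1/14 (most extreme randomization result) | p = 1/20, next participant must also succeed |
|---|---|---|---|
| 2 | 1 − 0.95² = 9.8% | 13.8% | 0.0975 × 0.05 = 0.5% |
| 3 | 1 − 0.95³ = 14.3% | 19.9% | 0.1426 × 0.05 = 0.7% |
| 4 | 1 − 0.95⁴ = 18.5% | 25.7% | 0.1855 × 0.05 = 0.9% |

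The chance of at least one success among k participants is the same whether or not the procedure changes. What a change alters is the denominator. Under a fixed procedure the result is 1 of k. Under alteration it can be presented as 1 of 1.

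**3. Loss of replications.** If the first change comes after participant j of an emotion, only participants 2 to j replicate the first. That is j − 1 replications where the design counts 5, and none if j = 1.

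**4. Change within a person.** Call the conditions A and B. The sequence A A B A B B is admissible. A change after session 2 leaves the first version with two A sessions and no B, and the second with one A and three B. Neither version has a 3 v 3 comparison, and the six-session result belongs to neither.

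**The case against.** The strongest reply is that flexible alteration is accepted single-case practice. The plan presents it as intervention development and describes Phase I as exploring. Instructions are already tailored to each person's urges, so what is replicated is a principle and not one fixed behaviour. The example change extends the behaviours used in both conditions, so the contrast between them remains. Phase II takes its content from an existing treatment module, so no stated step carries a wrongly credited Phase I version into treatment. All of this stands, and it limits the consequence. It does not answer the point, because Phase I also has a directional hypothesis with formal tests, and nothing says which participants developed a version and which tested it.

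Three stronger readings are tempting, and the documents do not support them:

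- *That alteration itself creates a 26% chance of a false success per emotion and 71% overall.* These are 1 − 0.95⁶ and 1 − 0.95²⁴, the chance of at least one null non-overlap among 6 or 24 people. They are identical if nothing is ever altered.
- *That Hypothesis 1 will be tested only on whichever version worked.* No passage says so. Conclusions are drawn for each individual, and nothing excludes participants run before a change. The plan is silent on selection.
- *That replication is optional throughout.* Five replications per emotion are planned for the unaltered procedure. Only confirmation of an altered strategy is worded as something that can be done.

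**Conclusion.** The point holds in a limited form and should be settled before Phase I starts. The plan permits alteration aimed at obtaining an effect, with no limit on timing or number, and has no rule that separates choosing a version from testing it. The harm depends on a change being made. If none is made, the planned replications stand, and participants run before a change still replicate the first.

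As an illustration of size, 2 to 4 versions with one participant each give a chance of about 10% to 19% that at least one null version shows complete non-overlap and is available to be credited. This rests on the assumptions listed in the working. It would be higher if either of two indices could count as success, and lower if both had to agree. The plan's trigger is also looser than non-overlap: it refers to reductions under inconsistent acting, not to a difference between conditions. The percentages therefore show scale and do not predict the trial's error rate.

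**What to change.** Add to the Phase I procedures and analysis sections:

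1. The procedure for both conditions is fixed within a participant's six sessions. Any change starts with the next participant and is logged, with its date and reason, as a new version. A version means the rule for generating instructions, so ordinary tailoring to a person's urges is not a new version.
2. A version adopted after seeing results is credited with an effect only if the effect is reproduced in later participants who were not used to choose it. Otherwise it is reported as exploratory.
3. The individual results of all 24 participants, labelled by version, are reported and counted in the conclusion on Hypothesis 1. Only participants under the same version are called replications.

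The third item does not need a pooled test, which the plan does not contain. The cost is wording and a version log, and no participants or sessions are added. There is a small downside: a changed version is credited one or more participants later, and one adopted for the last participant of an emotion stays exploratory for that emotion. The freedom to alter the procedure is kept.

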*Phase I Assessment.* The DIPD-IV and ADIS-5 (described above) will be used to confirm inclusion and exclusion criteria. The primary dependent variable in Phase I is the intensity of the discrete emotion induced.

Three convergent indices (self-report, behavioral, and physiological) will be used. **Self-report:** The Positive and Negative Affective Schedule-Expanded Form (PANAS-X) includes subscales measuring the intensity of the four discrete emotions represented in this study (fear, sadness, guilt, and anger). A Manipulation Check will be included asking participants to rate the extent to which they feel they were adherent to the prescribed strategy (acting consistent vs. inconsistent). **Behavioral:** The Facial Expression Coding System^58 (FACES) is a rater-coding system that yields information regarding the frequency, intensity, and duration of facial expressions. Participants' facial expressions will be video recorded throughout all study procedures and all tapes will be subsequently coded by trained undergraduate research assistants. The applicant will receive standard training in this protocol by [name], its creator and a collaborator on this project.

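### Phase I leaves FACES coders unmasked and the post-regulation scoring window undefined, so the facial index is open to condition-linked bias and to scoring the instructed act

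*Combined protocol and SAP*

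**What the plan says.** Under Phase I Assessment, the intensity of the induced emotion is the primary dependent variable. Its behavioural index is FACES, in which raters score how often, how strongly and for how long expressions appear. On filming and coding, the same section states: "facial expressions will be video recorded throughout all study procedures and all tapes will be subsequently coded by trained undergraduate research assistants".

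Under PHASE 1: ATD Component Procedures, the order of events is given: "Following each emotion induction, participants will be instructed to either act consistent or inconsistent with the emotion induced". The guilt examples of acting against an urge include "making small talk with confederates while acting inconsistent to urges to lash could include writing thank you notes". If no effect appears, the investigators may "extend the purview of behaviors to include emotion-consistent/inconsistent posture, and tone of voice".

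Under Phase I Data Analyses, the randomization tests use the mean change in self-reported intensity and in "clinician-rated facial emotional intensity from post-induction to post-regulation condition". This calls the facial raters clinicians, whereas Phase I Assessment says they are undergraduate assistants.

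**The concern.** Two separate problems can arise when whole-session tapes are coded without further rules.

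- **Coder bias.** A coder who can see which behaviour was carried out may score the later footage in line with the hypothesis.
- **Construct.** FACES scores expression. If the later score is taken while the participant is carrying out a social task, it may record compliance with the instruction and not the remaining emotion. Masking does not cure this; only a defined window does.

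At stake is how far the facial result supports the self-report result. Participants know which strategy they used, so self-report is unmasked. The Timeline section gives corroboration of self-report as the purpose of the non-self-report indicators. If the facial score can lean the same way for reasons other than emotion, agreement between the two is weaker independent evidence. Procedures may also be altered during the study when no effect is seen, so decisions within the study depend on these readings too.

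**Working it through.** The plan states no figure for this risk, so the check mainly sets the sections against each other.

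1. **What the tape covers.** Filming runs through all procedures (Phase I Assessment). The instruction and the instructed act follow the induction (ATD Component Procedures). Both therefore lie within the filmed period.

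2. **Masking.** No section masks FACES coders to condition, hypothesis or session order, and none mentions clipping, muting or shuffling. The one statement on rater blinding, under Phase II Assessment Quality Assurance, concerns the Phase II independent evaluators and says they need not be blind. The safeguard against expectancy in Phase I, presenting both strategies as credible, is addressed to participants.

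3. **Scoring window.** Phase I Data Analyses names two points, post-induction and post-regulation. It gives neither a start nor an end for either, and does not say whether the second excludes the act itself.

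4. **Does the design cancel a coder bias?** Let each session's score be the fall in facial intensity from post-induction to post-regulation. If knowledge of condition adds *b* to that fall in inconsistent sessions, then

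   expected difference in means = true effect + *b*.

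   Using change scores does not remove *b* if it enters only the post-regulation score. Randomizing the order does not remove it, because *b* follows the condition label.

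5. **Scale in the planned test (illustration).** Each participant has 3 sessions per condition, with no condition more than twice in a row.
   - Orders with 3 and 3: 6!/(3!3!) = 20.
   - Orders with three in a row: 4 + 4 − 2 = 6.
   - Allowed orders: 20 − 6 = 14, so the smallest one-sided p is 1/14 = 0.071.

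   Assume no true effect, independent normal session scores with SD 1, and a constant bias *b*. Simulating 40,000 participants per row gives:

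   | Assumed *b* (SD) | Chance of reaching p = 1/14 |
   |---|---|
   | 0 | 7% |
   | 0.2 | 10% |
   | 0.5 | 17% |
   | 0.8 | 26% |

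   The document gives no value for *b*; the range is assumed.

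6. **Standing of FACES.** Phase I Assessment announces three indices, including a physiological one, but describes no physiological measure. Study Overview lists only self-report and behavioural indices, and Phase I Data Analyses tests only those two. FACES is therefore the only non-self-report index that is both described and tested.

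**The case against.** The strongest reply is that silence is being read as a defect. The camera is aimed at the face, and the text does not say that sound or the spoken instruction is captured. Instructions depend on each person's own urges, so a coder who does not know the urge may not always recognise the condition. That stands: visibility of the condition is an inference, and a reader who concluded that every tape unmasks its coder would go beyond the document.

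Second, the analysis already contrasts post-induction with post-regulation, and the natural reading of the latter is after the strategy has ended. This limits the construct problem but does not remove it, because no boundary is set. Nor do all instructed behaviours drive the face: "making small talk with confederates" may do so, but writing thank-you notes or planning by email has no obvious facial demand. A claim that participants will look less upset whatever they feel is not supported.

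Third, a reader might infer that FACES is the only non-self-report index in Phase I. The document does name a physiological one, so the accurate statement is the narrower one about description and testing.

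Fourth, a reader might pool 24 × 3 = 72 sessions per condition and calculate an inflated false-positive rate. No such pooled test is planned. The analysis is by individual, combined with visual inspection, and with 14 allowed orders no single participant can reach a one-sided 5% level. Pooled rates should not be used to size this risk.

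None of this supplies the missing masking or the missing window.

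**Conclusion.** The point holds as an uncontrolled risk, not as proof of bias. Coding the tapes as written is likely to reveal the condition in many sessions, and some post-regulation scores may reflect the instructed behaviour. This rests on two readings: that filming throughout includes the instructed act, and that the absence of any coder-masking statement means none is planned. If the post-regulation score was always meant to come from footage after the act, the construct problem shrinks and the masking problem remains.

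The size is unknown. The single-participant figures only show the direction and rough scale of an assumed bias. The consequence is for interpretation: agreement between FACES and self-report would count for less as independent evidence. The plan should be changed, but the point does not invalidate Phase I. The disagreement over who rates the face, undergraduate assistants or clinicians, is a plain inconsistency to reconcile.

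**What to change.** Before coding starts, add to Phase I Assessment and Phase I Data Analyses:

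- The FACES score used in the randomization test comes from two fixed-length windows per session: one after the induction and before the instruction, and one after the instructed behaviour has ended.
- The windows are shown as muted clips under coded file names, shuffled across sessions and participants.
- Coders are unaware of condition and session number and do not code sessions that they ran.
- Both sections name the same raters.

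The cost is clip-cutting for 24 × 6 = 144 sessions (288 clips) by existing staff, with no change for participants. The person cutting the clips will know the session timing and so should not code them. Short windows may capture fewer expressions, which matters for frequency and duration scores. Footage outside the windows can be kept for descriptive use or for checking adherence, which at present rests on the participant's own rating.
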